### **Visit 22, Day 545 +/- 30 days**

This is the second data collection visit after the 12-month data collection from the main study (6m data collection visit for controls).

- Obtain fruit drink survey data, beverage intake data on the child participants using a validated questionnaire administered to the caregivers, plaque sample from children, hair samples and hair survey from each child participant, hair samples and hair surveys from the primary caregiver in the household (or another caregiver if the primary caregiver is not present), and side effects/adverse events from families in the intervention arm (see Appendix for surveys and instructions for self-collection of hair samples). Dietary 24 hour food recalls and food survey data may or may not be collected, for all participants, at the discretion of the PI.
- Conduct semi-structured interviews with caregivers about their family's consumption of sugared fruit drinks, consumption and availability of sugar-free alternatives, and their experiences throughout the intervention; along with post-study feedback on how the program went, any perceived changes in sugared fruit drink behaviors, difficulties and ways to improve the program (see Appendix and Manual of Procedures).
- Provide final instructions to participant (e.g., side effects, adverse events, how to contact with questions) (see Manual of Procedures).

## STUDY PROCEDURES/EVALUATIONS

### 7.1 Study Procedures/Evaluations

Study staff and CHWs will work with store staff in the 2 intervention communities to make sure the sugar-free water enhancers are available throughout the study period. This will involve the CHW visiting the stores weekly to monitor availability, to work with stores to order more if needed, to check with families to make sure they are not experiencing any difficulties finding or buying the drinks, and to problem solve with store owners to address any unanticipated barriers to families finding or buying the drinks. For all in-person study procedures, including store visits, the CHWs will use PPE and other precautions. UW study staff will also work with the store in the control community to make sure the sugar-free water enhancers are available throughout the control community intervention.

**Data Collection Frequency.** In all study communities, there will be 5 data collection visits (baseline, 1 month, 3 months, 6 months, and 12 months) which will take place separately from the intervention visits. In the control community, there will be 2 additional data collection visits (3-months and 6-months) after the initial 12-month study period.

**Data Collection Tools.** At the baseline data collection visit, demographic data, fruit drink survey data, 24-hour food recall and food question data will be collected for each participating child, a hair sample from the child(ren) and caregiver. All survey data will be collected electronically via laptop using a secure REDCap database, with survey data collection via phone in the case of remote implementation. The **demographic survey** will include standard questions found in national surveys that are validated (e.g., date of birth, race, household income, etc.). The **fruit drink survey** was developed by the study team and tested in the field with Yup'ik caregivers (see Manual of Procedures). The purpose of the fruit drink survey is to assess changes in knowledge, beliefs, and self-efficacy related to oral health, sugar-free drinks, and ability to help their children switch from sugared to sugar-free drinks. These measures will be part of the mediation analyses to assess for mechanisms underlying the intervention. For the 12-month data collection visit (and control community intervention data collection visits) the fruit drink survey may be completed by participants using a paper version of the survey form adapted from the versions on the REDCap database.

The **24-hour food recall**, a validated method, will be used to measure sugared fruit drink intake at baseline and 1-month. There will also be a **food survey** to measure food insecurity, breastfeeding, and other relevant questions related to food intake. Additional 24-hour food recall interviews and food surveys may or may not be conducted at 3-months, 6-months, and 12-months.

The **Beverage Questionnaire**, a validated beverage intake assessment tool (BEVQ-15) will be administered to caregivers to measure intake of several beverages for each of their enrolled children including: sugared fruit drinks, sweetened juice, 100% juice,

sugar-free Kool-Aid, soda pop/soft drinks, diet soda pop/artificially sweetened soft drinks (not including sugar-free Kool-Aid), sports drinks/energy drinks and milk. The

The **plaque sample** will be collected and banked at the UW for future analyses to determine the effects of the intervention on bacteria in the mouth. The **hair sample** will be used to measure added sugar intake using a validated biomarker (Nash et al. 2013). The hair sample is accompanied by a short **hair survey** regarding hair condition (e.g., bleached, dyed, etc.). The plaque sample will not be collected in case of remote study implementation.

A **side effects and adverse events form** will be used to record data on potential and other events that could come from excess intake of the sugar-free water enhancers, as a measure of safety, and to allow our team to intervene as needed to minimize any potential side effects associated with the intervention. This form will only be collected from intervention families.

At subsequent data collection visits, the same information will be collected except for demographic data, 24-hour food recalls, and food surveys. The 6-month and final visit (12-month) will include **semi-structured interviews** with caregivers to qualitatively assess perceived changes in sugared fruit drink consumption, behavior changes, obtain feedback about the program, benefits and drawbacks, and ways to improve the program. Incentives will be given at each data collection visit. For the 12-month data collection visit (and control community intervention data collection visits), some of the questions from the semi-structured interviews may be answered by participants using a paper-based survey, prior to the in-person interview.

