#### **6.4 Final Study Visit**

##### **Visit 14, Day 365 + 30 days**

This is the fourth data collection visit after the baseline visit (12 months).

- Obtain fruit drink survey data, beverage intake data on the child participants using a validated questionnaire administered to the caregivers, plaque sample from children, hair samples and hair survey from each child participant, hair samples and hair surveys from the primary caregiver in the household (or another caregiver if the primary caregiver is not present), and side effects/adverse events from families in the intervention arm (see Appendix for surveys and instructions for self-collection of hair samples). Dietary 24 hour food recalls and food survey data may or may not be collected, for all participants, at the discretion of the PI. The fruit drink surveys may be completed by participants using a paper version of the survey form adapted from the versions from the REDCap database.
- If visit conducted remotely, obtain survey data via phone and enter in REDCap and assist participants with collection of hair samples using kit mailed to them. Conduct the post-study interview and provide final instructions by phone. No plaque sample will be collected in case of remote study implementation.

- Conduct semi-structured interviews with caregivers about their family's consumption of sugared fruit drinks, consumption and availability of sugar-free alternatives, and their experiences throughout the intervention; along with post-study feedback on how the program went, any perceived changes in sugared fruit drink behaviors, difficulties and ways to improve the program (see Appendix and Manual of Procedures). Some of the questions from the semi-structured interviews may be answered by participants using a paper based survey, prior to the in-person interview.
- Provide final instructions to participant (e.g., side effects, adverse events, how to contact with questions) (see Manual of Procedures).
- Obtain consent and assent for families and children in the control arm who are interested in participating in the second phase of the study for the modified control community intervention.

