### 13.1 Final Analysis Plan

The analysis will be based on the intent to treat principle. Demographic variables will be summarized for the intervention arm and no-treatment arm at baseline and at each follow-up for all outcome measures and behavioral survey variables, as well as baseline demographics. Quantitative measures will be summarized by the mean and standard (or median and interquartile range for measures with a skewed distribution) and categorical measures will be summarized by frequency and percentage.

Linear regression analyses will be used to test if the average change in added sugar intake between baseline and 6 months is the same for children in the intervention arm and no-treatment control arm. A 2-sided 0.025 significance level will be used for the tests of the primary outcome. Generalized estimating equation (GEE) methodology will be used to fit the linear regression models using robust standard errors that account for potential clustering of outcomes within a household and allow for heteroscedasticity (Hardin and Hilbe 2003). Additional linear regression analyses will compare the 2 arms adjusted for baseline characteristics to assess for potential confounding and to assess for moderation of the intervention effect on child sugar intake by baseline characteristics, including child age, child sex, and traditional diet. In addition, to assess the effects of sex as a biological variable, separate estimates for the intervention effect on added sugar intake will be reported by child sex.

Similar linear regression analyses will be performed for the secondary outcomes for changes in caregivers' added sugar intake, knowledge, beliefs and self-efficacy. Outcomes at 1 month and 3 months will be summarized to elucidate the changes from baseline to 6 months in the intervention arm and no-treatment arm. Linear regression analyses will also be used to test the exploratory hypothesis that children in the intervention arm will have decreased sugared fruit drink intake after having received the intervention (at 6 months and 12 months).

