To assess the hypothesis that children in the intervention arm will have an altered oral microbiome, due to changes in sugared fruit drink and added sugar intake, data from a microbiome analysis of oral plaque samples collected at five data collection timepoints (baseline, 1 month, 3 month, 6 month and 12 month) will be used to compare changes in mutans streptococci levels and other oral microbiome features (e.g., species abundance, composition and diversity). Linear and log-linear regression will be used to test separately if there are changes in mutans streptococci levels and other oral microbiome features and to compare changes in children in the intervention versus control communities. Robust standard errors will be used with linear regression and log-linear regression to account for potential heteroscedasticity and overdispersion.

Similar analyses will be conducted on the 3m and 6m data collected from families in the control community who receive the modified intervention.

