## APPENDIX E: FRUIT DRINK SURVEY

(Please read to caregiver)

We are going to be talking about sugared fruit drinks: the kinds of drinks where you add a powdered mix to water. We will use Tang and Kool-Aid as examples of sugared fruit drinks, which could also include drinks like Hawaiian Punch and Country Time Lemonade. Keep in mind that we are not talking about soda pop or the warm Tang you give to your child when he/she is sick. For each statement, please choose whether you strongly agree, agree, have no opinion, disagree, or strongly disagree.

### Section 1

	Strongly agree	Agree	No opinion	Disagree	Strongly disagree
Tang and Kool-Aid are healthy for my child. [in general]					
It is important to limit how much Tang and Kool-Aid my child drinks.					
Watering down Tang and Kool-Aid makes them healthier. [adding more water than the package says so it's diluted]					
Preventing cavities is important.					
It is important for me to help my child to be cavity-free.					
Sugar-free drinks are unsafe					

[Present photo of sugar-free Tang and Kool-Aid to participants and say]: Here is a picture of sugar-free Tang and Kool-Aid.

Have you seen these drinks before?

Yes  
 No

**Here are some more statements regarding sugar-free Tang and Kool-Aid. Please answer whether you strongly agree, agree, have no opinion, disagree, or strongly disagree.**

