**Section 1A**

	Strongly Agree	Agree	No opinion	Disagree	Strongly Disagree
Sugar-free Tang and Kool-Aid are healthier than regular Tang and Kool-Aid.					
Sugar-free Tang and Kool-Aid are not as tasty as regular Tang and Kool-Aid.					

**The following statements are related to supervising/controlling your child's drink intake. For the following statements, please choose whether you strongly agree, agree, have no opinion, disagree, or strongly disagree.**

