## APPENDIX F: PAPER VERSION OF FRUIT DRINK SURVEY

REDUCING SUGARED FRUIT DRINKS IN ALASKA NATIVE CHILDREN  
FRUIT DRINK SURVEY  
SEPTEMBER 2023  
[«SURVEY\_»][«MATCH\_ID»]

*This section is to be completed by UW Study staff.*

DATE: \_\_\_\_ / \_\_\_\_ / \_\_\_\_ TIME: \_\_\_\_\_ COMMUNITY: «COMMUNITY»

Household ID: «HOUSEHOLD\_ID» Caregiver ID: \_\_\_\_\_ Child ID: «CHILD\_ID» Combined ID: \_\_\_\_\_

Please answer the questions on this form for this child [CHILD NAME: «FULL\_NAME»]

What is your relationship to this child [«FIRST\_NAME»]?

*Please circle one.*

Mother	Father	Grandmother	Grandfather	Aunt	Uncle	Other
--------	--------	-------------	-------------	------	-------	-------

These questions are about sugared fruit drinks. The kind where you add a powdered mix to water like Tang and Kool-Aid.

Keep in mind that we are not asking about soda-pop or the warm tang you may give your child when he/she is sick.

*For each of the following, please circle one response.*

Tang and Kool-Aid are healthy for my children, in general.	Strongly Agree	Agree	No Opinion	Disagree	Strongly Disagree
It is important to limit how much Tang and Kool-Aid my children drink.	Strongly Agree	Agree	No Opinion	Disagree	Strongly Disagree
Preventing cavities is important.	Strongly Agree	Agree	No Opinion	Disagree	Strongly Disagree
It is important for me to help my children to be cavity-free.	Strongly Agree	Agree	No Opinion	Disagree	Strongly Disagree
Sugar-free drinks are unsafe.	Strongly Agree	Agree	No Opinion	Disagree	Strongly Disagree

Quvana for your responses!

Page 1 of 4

REDUCING SUGARED FRUIT DRINKS IN ALASKA NATIVE CHILDREN  
FRUIT DRINK SURVEY  
SEPTEMBER 2023  
[«SURVEY\_»][«MATCH\_ID»]

Have you seen these drinks before?		Please circle one.
Tang and Kool-Aid  	Sugar-free Tang and Kool-Aid  	YES
		NO

These statements are about supervising/controlling your child's drink intake .					
For each of the following, please circle one response.					
I can get [«FIRST_NAME»] to drink less regular Tang and Kool-Aid.	Strongly Agree	Agree	No Opinion	Disagree	Strongly Disagree
I can get [«FIRST_NAME»] to drink sugar-free Tang and Kool-Aid.	Strongly Agree	Agree	No Opinion	Disagree	Strongly Disagree

Quvana for your responses!

Page 2 of 4

REDUCING SUGARED FRUIT DRINKS IN ALASKA NATIVE CHILDREN  
FRUIT DRINK SURVEY  
SEPTEMBER 2023  
[«SURVEY\_»][«MATCH\_ID»]

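### The paper fruit drink survey allowed from 12 months is not item-equivalent to the staff-read REDCap survey, so later values are only partly comparable with those from baseline to 6 months.

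*Combined protocol and SAP*

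**What the plan says.** Section 7.1 (Data Collection Tools) gives the survey's purpose as assessing change in knowledge, beliefs and self-efficacy. It then allows a second form, based on the REDCap one, at 12 months and in the control community's delayed phase: "the fruit drink survey may be completed by participants using a paper version of the survey form". Section 6.4 repeats the permission for Visit 14: "The fruit drink surveys may be completed by participants using a paper version of the survey form". The permission is optional and is not tied to an arm. Later in section 7.1, the protocol says that visits after baseline collect the same information, apart from demographics, 24-hour recalls and food surveys. The fruit drink survey is not among those exceptions.

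Appendix E is scripted for staff to read to the caregiver. Appendix F is for the caregiver to fill in, and all four of its numbered pages are present.

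Section 13.1 summarises results by arm "at baseline and at each follow-up for all outcome measures and behavioral survey variables", which includes 12 months. It closes with "Similar analyses will be conducted on the 3m and 6m data collected from families in the control community", meaning those given the modified intervention. It does not mention form or mode, and it defines no scoring rule for the survey.

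**The concern.** A survey meant to measure change needs the same questions, asked the same way, at each time point. Here the permitted form changes at the last main-study visit and in the delayed phase. Two of the three omitted items compare sugar-free with regular drinks, and section 5.1 says the health education highlights the benefits of sugar-free water enhancers. The awareness item is a natural indicator of exposure to the sugar-free products in the control community, and on paper it asks something different.

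The 12-month by-arm summaries, and any delayed-phase survey analysis, could therefore present a change of form as a change of belief or awareness. Because use is optional, form and mode can also differ between caregivers or communities at one visit.

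**Working it through.** **Inputs.** Appendices E and F compared item by item; the use of the survey taken from sections 2.3, 6, 7.1, 11.1.3 and 13.1. The plan gives no figure of its own to reproduce on this point.

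**Item count**

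| Block (Appendix E numbering) | REDCap | Paper |
|---|---|---|
| Section 1, agree/disagree | 6 | 5 |
| Awareness | 1 | 1 (changed) |
| Section 1A, sugar-free vs regular | 2 | 0 |
| Section 2, self-efficacy | 2 | 2 |
| Section 3, availability and other adults | 3 | 3 |
| Section 4, true/false | 3 | 3 |
| Gives sugared drinks, yes/no | 1 | 1 |
| Section 5, reasons | 9 | 8 |
| Section 5, open question | 1 | 1 |
| Gives sugar-free drinks, yes/no | 1 | 0 |
| Section 6, reasons | 7 | 0 |
| Section 6, open question | 1 | 0 |
| Total | 37 | 24 |

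- Knowledge, belief and self-efficacy items (Sections 1, 1A, 2, 4): 6 + 2 + 2 + 3 = 13 on REDCap; 5 + 0 + 2 + 3 = 10 on paper. Missing: 3/13 = 23%. If Section 3 is also counted, 3/16 = 19%.
- The three omitted items are "Watering down Tang and Kool-Aid makes them healthier", the statement that sugar-free versions are healthier than regular, and "Sugar-free Tang and Kool-Aid are not as tasty as regular Tang and Kool-Aid".
- Of the four belief or knowledge items about sugar-free drinks (unsafe, healthier, less tasty, cause cavities), 2 of 4 are absent.
- Whole form: 37 − 24 = 13 questions lost (3 + 1 + 1 + 7 + 1).

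**Retained items.** Of the 10, five keep their wording: preventing cavities, sugar-free drinks unsafe, and the three true/false items. Three move from the singular child to children in the plural, although section 2.3 has one survey completed per child. The two self-efficacy items insert the child's name. All 10 change from staff-read to self-completed.

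**Awareness item.** In Appendix E the question follows a photo of sugar-free products only. In Appendix F, "Have you seen these drinks before" has one yes/no answer beside two product headings, regular and sugar-free. A caregiver who knows only the regular product can answer yes on paper.

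**Effect on a score, if one were formed (assumption: the plan defines none)**
- Raw sum with identical answers and equal item averages: 10/13 = 76.9% of the REDCap value, a fall of 23.1%.
- Per-item mean: let f be the favourable proportion over all 13 items and d that over the three omitted. The retained mean is (13f − 3d)/10, so the shift is 0.3(f − d). For f from 0.5 to 0.8 and d from 0.2 to 1.0, it runs from 0.3(0.5 − 1.0) = −0.15 to 0.3(0.8 − 0.2) = +0.18. It is zero when d = f.
- Item-level analysis: no shift from the omission; three items are simply missing.

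**Effect on the 12-month arm contrast.** Suppose form moves a retained item by δ in either arm, and proportions p_I and p_C use paper. The contrast is then biased by δ(p_I − p_C), which is zero when use is equal.

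**Which planned analyses use paper data**
- Exploratory hypothesis 1 (section 11.1.3) is tested at the end of the intervention: no.
- Mediators (section 13.1) are changes from baseline to 6 months: no.
- By-arm summaries at 12 months (section 13.1): yes, where paper is used.
- Delayed-phase survey data (Visits 21 and 22): yes, where paper is used and if the repeated analyses cover the survey.

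**The case against.** A reader might infer that all 12-month and delayed-phase survey values shift by construction. The documents do not support that. A mechanical shift follows only for a raw summed score, and no score is defined. Item by item, the omitted questions are missing and the other ten are not moved by their absence. Mode and wording effects on those ten are possible but not shown.

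A reader might also infer that the arm comparison is biased. The permission covers both arms, so on common items distortion needs different uptake by arm. The optional wording allows that, but nothing in the documents shows it.

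Other objections have weight:
- The plan has no main-study test of the survey measures at 12 months, only a descriptive summary.
- The sentence on repeating analyses follows the microbiome paragraph, so its reach to the survey is unclear.
- The 12-month visit is Day 365 and the control intervention starts on Day 366. The 12-month survey is therefore a natural delayed-phase baseline and could be on the same paper form. The plan does not say it will be.
- The Appendix F pictures are missing from the extract, so the awareness layout is read from its headings and answer cells.
- The health education description names neither dilution of regular drinks nor taste, so not every omitted item is a stated target.

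These points narrow the concern. They do not remove the item differences, or the conflict with the statement in section 7.1 that later visits collect the same information.

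**Conclusion.** The point stands in limited form. The two forms are not item-equivalent: 3 of 13 knowledge, belief and self-efficacy items and 13 of 37 questions overall are absent on paper. The 13 rests on grouping Sections 1, 1A, 2 and 4 as the constructs, which the plan does not spell out.

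Where paper is used, the omitted items have no values, and the awareness item cannot be compared with baseline to 6 months. The awareness conclusion assumes that the printed page matches the extracted layout. For the ten retained items, the size and direction of any mode or wording effect are unknown.

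The damage is confined to the 12-month summaries and to any delayed-phase survey analysis. This is worth correcting because the remedy is cheap, but it does not threaten the 6-month test of exploratory hypothesis 1 or the mediators.

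**What to change.** Align Appendix F with Appendix E. Restore the three omitted items, the missing Section 5 reason, the sugar-free-use question and Section 6, and ask the awareness question about sugar-free products only. Restoring the three belief items alone would not make the forms equivalent. Use one form for all caregivers at a given visit.

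Where the paper form has already been used, add to section 13.1:
- Form and mode are recorded for every survey.
- Comparisons across forms use only the 10 common items and exclude the awareness item.
- The 12-month survey is the delayed-phase baseline when it was on the same form as the later visits.
- The change of mode is reported as a limitation.

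An indicator for form should not be relied on as the correction. If every 12-month survey is on paper and none before, it is collinear with visit. If only the control community uses paper at a visit, it is collinear with arm at that visit. The baseline-to-6-month analyses keep all 13 items.

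The cost is a paper form longer by up to 13 questions, or a few sentences in section 13.1 and fewer items in later comparisons.

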## **Visit 4, Day 30 + 7 days**

This is the first data collection visit after the baseline visit (1 month).

- Obtain fruit drink survey data, 24-hour food recall and food survey data for each enrolled child, plaque sample from child, hair sample and hair survey from each child participant, hair sample and hair survey from the primary caregiver in the household, and side effects/adverse events (see Appendix for surveys and instructions for self-collection of hair samples).
- If visit conducted remotely, obtain survey data via phone and enter in REDCap and assist participants with collection of hair samples using kit mailed to them. No plaque sample will be collected in case of remote study implementation.

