### **Visit 8, Day 90 ± 7 days**

This is the second data collection visit after the baseline visit (3 months).

- Obtain fruit drink survey data, optional 24-hour food recall and food survey data for each enrolled child, plaque sample from children, hair samples and hair survey from each child participant, hair samples and hair surveys from the primary caregiver in the household (or another caregiver if the primary caregiver is not present), and side effects/adverse events for intervention families (see Appendix for surveys and instructions for self-collection of hair samples). Dietary 24 hour food recalls and food survey data may or may not be collected, for all participants, at the discretion of the PI. If visit conducted remotely, obtain survey data via phone and enter in REDCap and assist participants with collection of hair samples using kit mailed to them. No plaque sample will be collected in case of remote study implementation.

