## **8.3 Adverse Events**

An adverse event is any untoward or unfavorable medical occurrence in a human participant, including any abnormal sign (for example, abnormal physical exam or laboratory finding), symptom, or disease, temporally associated with participation in the research, whether or not considered related to participation in the research.

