## **8.5 Time Period and Frequency for Event Assessment and Follow-Up**

The PI will record all events with start dates occurring any time after informed consent is obtained until 7 (for non-serious AEs) or 30 days (for SAEs) after the last day of study participation. At each study visit, the Community Health Worker or Study Staff will inquire about the occurrence of AE/SAEs since the last visit. Events will be followed for outcome information until resolution or stabilization.

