## **8.8 Halting Rules**

If there is a significant number of children who experience symptoms or side effects that are thought to be associated with the sugar-free water enhancers (more than 20%), an ad hoc safety review will be convened. The objective of the safety review is to decide whether the study (or intervention for an individual or study cohort) should continue per protocol, proceed with caution, be further investigated, be discontinued, or be modified and then proceed. Suspension of enrollment (for a particular group, a particular study site, or for the entire study) is a potential outcome of a safety review.

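### Adverse-event collection in the control arm is contradictory and has no assigned form, so no background rate of stomach symptoms is assured for the relatedness judgement behind the 20% review trigger

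*Combined protocol and SAP*

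**What the plan says.** The protocol gives two sets of instructions on who is asked about adverse events.

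**Limited to the intervention arm.** Section 7.1 says of the side-effects and adverse-events form (Appendix J): "This form will only be collected from intervention families". The 3-month visit lists "side effects/adverse events for intervention families", and the 6-month visit uses the same words. The 12-month visit lists "side effects/adverse events from families in the intervention arm".

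**Not limited by arm.** Section 8.3 defines an adverse event "whether or not considered related to participation in the research". Section 8.5 states: "The PI will record all events with start dates occurring any time after informed consent is obtained", and adds: "At each study visit, the Community Health Worker or Study Staff will inquire about the occurrence of AE/SAEs since the last visit". The 1-month visit lists "hair sample and hair survey from the primary caregiver in the household, and side effects/adverse events" with no arm named.

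**Internally inconsistent.** Visits 21 and 22 take place only in the control community, yet their text repeats the 12-month wording about families in the intervention arm. The control schedule in Appendix A marks side effects in that later phase.

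The baseline visit (6.2) lists no symptom or side-effect item. Section 8.8 sets the safety trigger on the share of children whose symptoms are attributed to the enhancers: "more than 20%), an ad hoc safety review will be convened". It gives no denominator, time window or background rate. The final analysis plan (13.1) contains no safety analysis.

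**The concern.** Appendix J opens by asking about upset stomach, runny stool and diarrhea. These are non-specific and can occur without the product. To judge whether a given count points to the enhancers, one needs to know how often the same question would draw a yes from children who are not drinking them. As written, the plan assures neither a concurrent rate from Community C nor a pre-exposure rate from Communities A and B.

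Two things are at stake. Staff in Community C cannot follow both 7.1 and 8.5, so what is recorded there may depend on which section is read. And those who judge relatedness, convene the review or sit on the DSMB would do so without a comparator.

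**Working it through.** **1. The passages side by side**

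| Place | Limit by arm |
|---|---|
| 7.1 (form) | Intervention families only |
| 3-, 6- and 12-month visits | Intervention families only |
| 1-month visit | None stated |
| 8.3, 8.5 | None stated |
| Visits 21 and 22 (control community only) | Text names the intervention arm |
| Baseline (6.2) | No symptom item for either arm |

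Section 8.6 calls for an appropriate case report form, but the protocol names none for routine events in controls. Data from Visits 21 and 22 would in any case follow exposure to the enhancers, so they could not supply a background rate.

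**2. The 20% trigger as a count**

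The plan gives no derivation for the 20%, so there is no figure to reproduce. Taking the 136 intervention children as denominator (an assumption, since 8.8 names none): 0.20 × 136 = 27.2, so more than 20% means at least 28 children (28/136 = 20.6%). With all 192 enrolled: 0.20 × 192 = 38.4, so at least 39.

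**3. How the trigger behaves when the product does nothing**

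Let B be the share of children with any background stomach symptom over follow-up and f the fraction of those attributed to the drinks. The attributed share is B × f, and the chance of a review is P(X ≥ 28) for X binomial(136, B × f). Both B and f are assumptions; the documents give neither.

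| B × f | Example | Chance of reaching 28 of 136 |
|---|---|---|
| 10% | B 20%, f one half | 0.02% |
| 15% | B 30%, f one half | 4.8% |
| 20% | B 40%, f one half | 46.6% |
| 25% | B 50%, f one half | 90.3% |

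Household clustering is ignored. The result runs from negligible to near certain over a range that the planned data would not narrow.

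**4. What a control rate would buy**

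The 95% half-width for the difference between arms, with a common rate p = 0.20, is 1.96 × √[p(1−p)(1/n₁ + 1/n₂)]. The design effect uses the plan's household size of 2.15 (SD 1.23) and intra-family correlation of 0.3: CV² = (1.23/2.15)² = 0.327, and 1 + [(0.327 + 1) × 2.15 − 1] × 0.3 = 1.556, whose square root is 1.247.

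- Full follow-up, 136 v 56: 1.96 × √[0.16 × (1/136 + 1/56)] = 0.124; with clustering 0.124 × 1.247 = 0.155.
- 25% attrition (the plan's upper figure), 102 v 42: 1.96 × √[0.16 × (1/102 + 1/42)] = 0.144; with clustering 0.144 × 1.247 = 0.179.

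**5. Recall periods under the current wording**

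Appendix J asks about the time since the previous visit. On the Study Schedule:

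- 3 months (Day 90): intervention families were last seen at Day 75, 15 days back; controls at Day 30, 60 days back.
- 6 months (Day 180): intervention families at Day 165, 15 days back; controls at Day 90, 90 days back.

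Giving the form unchanged to controls would therefore make the intervention arm look better by construction.

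**The case against.** The two sets of passages can be partly reconciled. Section 7.1 describes a form aimed at excess intake of the enhancers, and much of Appendix J asks who mixed the drink, how it was stored and whether the card was exceeded. Those items mean nothing for unexposed controls. Control events could go on another form under 8.6. This stands in part: control events need not go unrecorded. But no such form is named in the protocol, and the 3-, 6- and 12-month texts omit the inquiry itself for controls, not just the form.

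The trigger also has safeguards. Section 8.6.1 gives causality criteria, 8.1 has the investigator work with the caregiver and a medical health aide on cause, and a DSMB reviews safety. This stands too, and it would be wrong to say that the trigger rests on unmasked opinion alone. The criteria do not replace a comparator, however. An event can be classed as related because it is known to occur with the intervention or follows it in time, and 8.1 already lists stomachache and diarrhea as side effects. An unrelated stomach upset can meet that test.

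Finally, no objective or hypothesis claims comparative safety. That is correct, so the missing control rate does not defeat a stated aim.

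Two stronger readings are tempting, and the documents do not support either:

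- **That controls are never asked.** The 1-month text and 8.5 carry no arm limit. What can be said is that control ascertainment is contradictory.
- **That background symptoms alone would trip the trigger.** With 11 inquiries (Visits 4 to 14) and an assumed 2% to 5% per interval, 1 − 0.98¹¹ = 19.9% and 1 − 0.95¹¹ = 43.1% of children would report something. That counts any symptom, whereas 8.8 counts only attributed ones, so it assumes every symptom is attributed. It also assumes independence and one constant risk over intervals from 15 days (Day 30 to 45) to 185 days (Day 180 to 365). Its low end is below the threshold, and the documents give no background rate.

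**Conclusion.** The concern holds as a contradiction in the text and a missing reference rate. The contradiction needs no assumption: 7.1 and the 3-, 6- and 12-month visits cannot be followed together with 8.5, and Visits 21 and 22 name an arm that is not there. It also follows from the text that no background rate is assured, with the reservation that the Manual of Procedures, which is not among the documents, might name a control instrument.

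The effect on the trigger is conditional. It rests on assumed values of background risk and attribution, on 136 as denominator and on independent children. Within those limits, a modest change in the attributed share, from 15% to 25%, moves the chance of a review without any product effect from about 5% to about 90%. A reader might infer that a false signal would halt the trial. It would not: 8.8 convenes a review, and continuing per protocol is one of its outcomes. The point is worth correcting but does not threaten the primary analysis.

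**What to change.** 1. Reconcile 7.1, the 3-, 6- and 12-month visit texts, Visits 21 and 22 and Appendix A with the 1-month visit text and 8.5, and name the form on which control events are recorded.
2. At the 1-, 3-, 6- and 12-month data visits, ask caregivers in both arms the symptom and severity questions of Appendix J, leaving out the drink-mixing items for controls.
3. Use the same fixed look-back period in both arms at those visits, in place of the time since the previous visit.
4. Add to 13.1 a report of symptom rates by arm at those common visits, with intervals that allow for households.

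None of this alters the 20% threshold or the management of symptoms.

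The cost is a few extra questions for control families at visits already scheduled in Community C, and a small amendment needing IRB approval under 16.1. No visit or staff member is added.

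The result should be presented as a rough reference. It comes from one non-randomized, unmasked control community, and at a 20% rate the difference would be known only to within about 12 points (16 with household clustering) at full follow-up, or about 14 (18) at 25% attrition.
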